6.2 Randomization Procedures

- 6.21 To register a patient, access the ACCRU web page at [REDACTED] go to the Study Resources → Application section and click on “Registration” and enter the registration/randomization application. The registration/randomization application is available 24 hours a day, 7 days a week. Back up and/or system support contact information is available on the Web site. If unable to access the Web site, call the Academic and Community Cancer Research United (ACCRU) Registration Office at email [REDACTED] between the hours of 8 a.m. and 4:30 p.m. Central Time (Monday through Friday).

Instructions for the registration/randomization application are available on the above web page under the Study Resources section → Application section. Please refer to the “Research Registration Application Training” or Quick Reference Guide for instructions.

Prior to initiation of protocol study intervention, this process must be completed in its entirety and an ACCRU subject ID number must be available as noted in the instructions. It is the responsibility of the individual and institution registering the patient to confirm the process has been successfully completed prior to release of the study agent. Patient registration via the registration/randomization application can be confirmed in any of the following ways:

- Contact the ACCRU Registration Office at [REDACTED] If the patient was fully registered, the ACCRU Registration Office staff can access the information from the centralized database and confirm the registration.
 - Refer to the Research Registration Application training on the ACCRU website under Study Resources → Applications.

6.22 Prior to accepting the registration, the registration application will verify the following:

- IRB approval at the registering institution
- Patient eligibility
- Existence of a signed consent form
- Existence of a signed authorization for use and disclosure of protected health information

6.23 Correlative Research

Mandatory

A mandatory correlative research component is part of this study. The patient will be automatically registered onto this component (see Sections 3.0, 14.0 and 17.0).

Optional

An optional correlative research component is part of this study. There will be an option to select if the patient is to be registered onto this component (see Section 14.0).

- Patient has/has not given permission to give his/her blood sample for research testing.

6.24 At the time of randomization, the following will be recorded:

- Patient has/has not given permission to store and use his/her blood sample(s) for future research to learn, prevent, or treat cancer.
- Patient has/has not given permission to store and use his/her blood sample(s) for future research to learn, prevent, or treat other health problems (for example: diabetes, Alzheimer’s disease, or heart disease).
- Patient has/has not given permission to store and use his/her

tissue sample(s) for future research to learn about, prevent, or treat cancer.

- Patient has/not given permission to store and use his/her tissue sample(s) for future research to learn, prevent, or treat other health problems (for example: diabetes, Alzheimer's disease, or heart disease).
- Patient has/not given permission for ACCRU to give his/her sample(s) to outside researchers.

6.25 Treatment cannot begin prior to randomization and must begin ≤ 14 days after randomization.

6.26 Pretreatment tests/procedures (see Section 4.0) must be completed within the guidelines specified on the test schedule.

6.27 All required baseline symptoms (see Section 10.52) must be documented and graded.

6.28 Treatment on this protocol must commence at an ACCRU institution under the supervision of a medical oncologist.

6.29 a Study drug is available on site.

6.29b Blood draw kit is available on site.

6.3 Randomization Procedures

6.31 The factors, defined in Section 5.0, together with the registering membership, will be used as stratification factors.

6.32 After the patient has been registered into the study, the values of the stratification factors will be recorded, and the patient will be assigned to one of the two treatment groups using the Pocock and Simon [39] dynamic allocation procedure which balances the marginal distributions of the stratification factors between the treatment groups. At entry, physicians must declare whether each patient will receive irinotecan in protocol treatment (ie, irinotecan+anti-EGFR therapy versus anti-EGFR therapy alone). The stratification factors is defined as 6.21.

6.4 Sequential Treatment Phase

NOTE: Re-registration must occur ≤ 28 days from documentation of progression or intolerance.

6.41 Upon local confirmation of progression or intolerance, patients will be allowed to re-registered to receive the sequential treatment in the treatment arm.

6.42 To re-register a patient, email [REDACTED] a completed sequential treatment phase eligibility checklist to the Academic and Community Cancer Research United (ACCRU) Registration Office between 8 a.m. and 4:30 p.m. central time Monday through Friday.

- 6.43 Treatment cannot begin prior to re-registering to the sequential treatment phase and must begin \leq 7 days after registration for the sequential treatment phase.

7.0 Protocol Treatment

Drugs will be administered in accordance with the information on the respective package inserts. Treatment will be given according to the schedule specified in the protocol. The terms “delay,” “modification,” and “omission” are defined as follows:

Delay: A delay indicates dose was postponed or not received when expected.

Modification: Indicates a change in dose level during the current cycle. However, if a modification was issued after the last dose was received in the current cycle, the modification should be reported on the subsequent cycle.

Omission: Indicates a dose was skipped and not made up, or that the drug was discontinued.

Arm A, treatment with regorafenib followed by anti-EGFR therapy (\pm irinotecan).

Arm B, treatment with anti-EGFR therapy (\pm irinotecan) followed by regorafenib.

Treatment on regorafenib will be continued in accordance with Section 7.11 “Planned treatment with regorafenib” until any of the “Criteria for discontinuing treatment with regorafenib” (Section 8.34) is met.

Treatment on Anti-EGFR therapy (\pm irinotecan) will be continued in accordance with Section 8.4, “Combination therapy of Anti-EGFR therapy (cetuximab (Cmab) **OR** panitumumab (Pmab) and irinotecan” until any of the “Criteria for discontinuing treatment including Cmab or Pmab” (Section 8.44) is met.

Patients assigned to Anti-EGFR therapy will receive either cetuximab or panitumumab per treating physician discretion and will be dosed per prescribing guidelines. Patients cannot switch between cetuximab and panitumumab during the course of the study. The use of irinotecan is per treating physician discretion and will be dosed per prescribing guidelines. If treating physician chooses to add irinotecan, irinotecan must be included in treatment starting at cycle 1.

7.1 Treatment Schedule - Use actual weight or estimated dry weight if fluid retention

Agent	Dose	Route	Frequency	ReRx
Regorafenib	80mg daily (Starting dose) See table 7.11	PO	Daily for Days 1-21 of 28 day cycle	Every 28 days
Cetuximab*	500mg/m ²	IV	Days 1, 15	Every 28 days
Panitumumab*	6mg/kg	IV	Days 1, 15	Every 28 Days
Irinotecan	180mg/m ²	IV	Days 1, 15	Every 28 days

* Patients assigned to Anti-EGFR therapy will receive **EITHER** cetuximab **OR** panitumumab, not both

7.11 Planned treatment with regorafenib

Regorafenib Dose Escalation

Cycle 1:

Week	Dose ¹
1 Starting Dose	80 mg*
2	120 mg
3	160 mg
4	Off

***starting dose level**

1 Dose escalation/reduction should follow section 8.1

Cycle 2 and beyond:

Week	Dose
1	Remain at highest tolerated dose from Cycle 1 (up to 160 mg)
2	
3	
4	Off

Regorafenib tablets should be taken once a day with approximately 8 fluid ounces (240 mL) of water after a low-fat (<30% fat) meal. Regorafenib should be taken with a meal at the same time every day. Some examples of low fat meals are:

- Two slices of white toast with 1 tablespoon of low-fat margarine and 1 tablespoon of jelly and 8 ounces (240 mL) of skim milk (approximately 319 calories and 8.2 g of fat).
- One cup of cereal (i.e. Special K), 8 ounces (240 mL) of skim milk, one piece of toast with jam (no butter or marmalade), apple juice, and one cup of coffee or tea (2 g fat, 17 g protein, 93 g of carbohydrate, 520 calories).

If vomiting occurs shortly after regorafenib are swallowed, the dose should only be replaced if all of the intact tablets can be seen and counted. Should any patient enrolled on the study miss a scheduled dose for whatever reason (e.g. as a result of forgetting to take the tablets or vomiting), the patient will be allowed to take the scheduled dose up to a maximum of 2 hours after that scheduled dose time. If greater than 2 hours after the scheduled dose time, the missed dose is not to be taken and the patient should take their allotted dose at the next scheduled time.

7.2 Planned treatment with Anti-EGFR therapy (cetuximab (Cmab) or panitumumab (Pmab)) and irinotecan. Refer to 8.4 for treatment initiation requirements.\

7.21 Dose levels of panitumumab and cetuximab

Dose reduction level	Dose of panitumumab	Dose of cetuximab
Initial dose level	6 mg/kg	500 mg/m ²
-1	4.8 mg/kg	400 mg/m ²
-2	3.6 mg/kg	300 mg/m ²
-3	2.4 mg/kg	200mg/m ²

7.22 Dose levels of irinotecan

Dose reduction level	Dose of irinotecan
Initial dose level	180 mg/m ²
-1	150 mg/m ²
-2	120 mg/m ²
-3	100 mg/m ²

- 7.3 Study treatment with regorafenib, cetuximab, panitumumab, and Irinotecan may be administered up to 3 days before or after the scheduled Day 1, Day 15 of each cycle due to administrative reasons.

NOTE: Future treatment dates may need to be adjusted as a result of the ±3 days.

8.0 Dosage Modification Based on Adverse Events

Strictly follow the modifications in the following tables for the first **two** cycles, until individual treatment tolerance can be ascertained. Thereafter, these modifications should be regarded as guidelines to produce mild-to-moderate, but not debilitating, side effects. If multiple adverse events are seen, administer dose based on greatest reduction required for any single adverse event observed. Reductions or increases apply to treatment given in the preceding cycle and are based on adverse events observed since the prior dose.

ALERT: *ADR reporting may be required for some adverse events (See Section 10)*

8.1 Regorafenib Dose Escalation/Reduction

Dose level	If No SDRT	If + SDRT**
80 mg*	Proceed to next dose level	-
120 mg	Proceed to next dose level	Decrease to 80 mg
160 mg	-	Decrease to 120 mg

*starting dose level

**SDRT = Significant Drug Related Toxicities

- 8.11 After week 8, if toxicities have resolved to ≤ Grade 0-1, re-escalation is allowed 40 mg at a time every 4 weeks to a maximum of 160 mg and at the discretion of the treating physician.
- 8.12 Patients with dose reductions below 80 mg should go off treatment and go to event monitoring.
- 8.13 Any patients with toxicities requiring >4 week delay should go off treatment and then to event monitoring.

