8.2 Regorafenib Dose Modifications

8.21 Regorafenib may be dose reduced per the table 8.21 in case of intolerable toxicity such as weight loss, fatigue, rash or anorexia.

Table 8.21 Recommended dose modification for toxicities except hand-foot-skin reaction, hypertension and ALT/AST/bilirubin			
NCI-CTCAE v5.0^a	Dose Delay	Dose Modification ^b	Dose for Subsequent Cycles
Grade 0-2	Treat on time	No change	
Grade 3	Delay until \leq Grade 2 ^c	Reduce by 1 dose level	If toxicity remains $<$ Grade 2, dose re-escalation can be considered at the discretion of the treating physician. If dose is re-escalated and toxicity (\geq Grade 3) recurs, institute permanent dose reduction.
Grade 4	Delay until \leq Grade 2 ^c	Reduce by 1 dose level. Permanent discontinuation can be considered at treating physician's discretion.	

^a NCI-CTCAE = National Cancer Institute - Common Terminology Criteria for Adverse Events, version 5.0
^b Excludes alopecia, non-refractory nausea/vomiting, lymphocyte count decreased, non-refractory hypersensitivity and nonclinical and asymptomatic laboratory abnormalities.
^c If no recovery after a 4 week delay*, treatment should be permanently discontinued unless subject is deriving clinical benefit.
* Modify according to study specific cycle length

If greater than 2 dose level reductions are required, regorafenib will be discontinued and the rest of the study follow up may be continued. The following tables outline dose adjustments for toxicities related to regorafenib except hand-foot skin reaction, hypertension and liver function test abnormalities.

The table above outlines dose adjustments for hematologic and non-hematologic toxicities related to regorafenib except PPES and hypertension. In addition to these recommended dose modifications, subjects who develop diarrhea, mucositis, anorexia or other events predisposing to fluid loss or inadequate fluid intake should be carefully monitored and rehydrated as clinically necessary. This is in order to minimize the risk of postural hypotension and renal failure.

8.22 Regorafenib may be dose reduced per Table 8.22b in case of Palmar-plantar erythrodysesthesia using Table 8.22a for grading guidelines.

Table 8.22a: Grading for Palmar-plantar erythrodysesthesia syndrome			
	Grade 1	Grade 2	Grade 3

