a. More conservative management is allowed if judged medically appropriate by the treating physician.
 b. If toxicity returns to Grade 0-1 after dose reduction, dose re-escalation is not permitted.
 c. If there is no recovery after a 4-week delay, treatment with regorafenib will be discontinued permanently.
 d. Subjects requiring > 2 dose reductions should go off protocol therapy.
 e. The maximum daily dose is 160 mg.
 f. Refer to Section 9.0 for management strategies for Palmer-plantar erythrodysesthesia syndrome reactions.

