
a. Patients requiring a delay of >4 weeks should go off protocol therapy If BP remains controlled for at least one cycle. Patients requiring >2 dose reductions should go off protocol therapy.
 
b. If BP remains controlled for at least one cycle, dose re-escalation permitted per treating physician's discretion.
 
c. Patients requiring >2 dose reductions should go off protocol therapy.
		

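### Sections 8.12 and 8.13 do not separate initial from sequential regorafenib, so for Arm A they conflict with the crossover that 6.41, 8.6 and 13.6 provide

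*Combined protocol and SAP*

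**What the plan says.** Section 8.1 carries two rules in numbered text below the dose table. Section 8.12: "Patients with dose reductions below 80 mg should go off treatment and go to event monitoring". Section 8.13: "Any patients with toxicities requiring >4 week delay should go off treatment and then to event monitoring". Neither mentions arm or treatment phase.

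Elsewhere in section 8, similar triggers have a narrower consequence. The text under Table 8.21 reads: "If greater than 2 dose level reductions are required, regorafenib will be discontinued and the rest of the study follow up may be continued". Note c to Table 8.22b reads: "If there is no recovery after a 4-week delay, treatment with regorafenib will be discontinued permanently". Section 8.3 discontinues regorafenib if the dose must fall below level -2 or treatment cannot be resumed within 28 days. It does not mention event monitoring.

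A third group of notes lies in between. Note d to Table 8.22b: "Subjects requiring > 2 dose reductions should go off protocol therapy". Notes a and c to Table 8.23: "Patients requiring a delay of >4 weeks should go off protocol therapy" and "Patients requiring >2 dose reductions should go off protocol therapy". These name no destination.

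Four provisions deal with what follows a stop of the initial drug:
- Section 6.41 allows re-registration after progression or intolerance.
- Section 8.6 item 1 ends protocol treatment only when the sequential drug cannot follow within 28 days.
- Section 13.6 offers re-registration or event monitoring at the physician's choice.
- Footnote 12 of table 4.1 states re-registration as what will happen.

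**The concern.** The trial compares two sequences, so what happens when the first drug is not tolerated is part of the assigned treatment. In Arm B regorafenib comes last, and event monitoring is the right next step. In Arm A it comes first, and the same sentence leads past the second drug. The text gives three destinations for one intolerant Arm A patient: event monitoring (8.12, 8.13), the physician's choice (13.6) or re-registration (table 4.1, footnote 12). No rule of precedence is stated, so sites could handle the same case differently.

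The situation is not remote. Regorafenib starts at 80 mg, which is also the lowest dose. The 8.1 table shows only a dash for significant toxicity at 80 mg, so 8.12 is the only instruction in 8.1 for that case.

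Three secondary endpoints are at stake:
- PFS2 starts at re-registration (16.322), so a patient sent to event monitoring has none.
- The sequential response rate counts only patients who started the sequential drug (16.325).
- stPFS is censored at the last evaluation before the initial drug was stopped (16.323). That censoring would follow toxicity and be imposed by rule in one arm only.

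**Working it through.** **1. The plan's own figures.** These come first because the conclusion is that they do not move. Inputs from 16.22 and 16.23: medians 7.5 and 14.5 months, one-sided alpha 0.1, power 80%, 42 deaths, 26 evaluable patients per arm.
- HR = 7.5/14.5 = 0.517; ln HR = -0.659.
- Events (Schoenfeld) = 4(1.2816 + 0.8416)² / 0.659² = 41.5, rounded up to 42.
- Power at 42 events = Φ(0.659·√42/2 - 1.2816) = 0.804.
- Critical HR = exp(-1.2816·2/√42) = 0.673.

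All agree with the plan. An unstratified log-rank simulation (26 per arm, cut at 42 deaths, 20,000 runs) gives 79.4%, the figure in 16.24. None of these depends on the wording of 8.12 or 8.13.

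**2. The rules side by side.**

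| Place | Trigger | Consequence as written |
|---|---|---|
| 8.12 | dose below 80 mg | off treatment, event monitoring |
| 8.13 | delay over 4 weeks | off treatment, event monitoring |
| 8.3 | below level -2; not resumed in 28 days | regorafenib stopped |
| Text under Table 8.21 | more than 2 reductions | regorafenib stopped |
| Table 8.22b note c | no recovery after 4 weeks | regorafenib stopped |
| Table 8.22b note d; Table 8.23 notes a, c | more than 2 reductions; delay over 4 weeks (note a) | off protocol therapy, destination not named |
| 8.44 (anti-EGFR) | not resumed in 28 days | anti-EGFR drug stopped |

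Four weeks is 28 days, so 8.13 and 8.3 share a trigger. Regorafenib levels -1 and -2 are not labelled. Reading them as 120 mg and 80 mg, down from the 160 mg maximum, is an inference; on that reading 8.12 and 8.3 also share a trigger.

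**3. One patient in each arm, delayed over 4 weeks on the initial drug.**
- Arm A: 8.3 stops regorafenib; 8.6 item 1, 6.41 and 13.6 then leave anti-EGFR open. Section 8.13 sends the same patient to event monitoring.
- Arm B: 8.44 stops the anti-EGFR drug; 8.6 item 1, 6.41 and 13.6 leave regorafenib open. No text corresponds to 8.13.

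The conflict on initial treatment therefore exists in Arm A only.

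**4. Scale, on assumptions.** The documents give no rate for these triggers. Section 1.5 gives 8.2% for all drug-related stops in CORRECT. Assume that 2% to 8.2% of Arm A meet a trigger and that 25% to 100% of those are handled under 8.12 or 8.13. Expected patients affected:
- Low: 26 × 0.02 × 0.25 = 0.13
- Middle (5% and 50%): 26 × 0.05 × 0.50 = 0.65
- High: 26 × 0.082 × 1.00 = 2.13

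Each patient is 1/26 = 3.8% of the evaluable arm.

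**5. Power if crossover were lost.** Suppose a share of Arm A is denied crossover and has the control median of 7.5 months. Simulated power is then 75.8% at a share of 5% and 74.0% at 8.2%, against 79.4% at zero. Both the share and the survival of these patients are assumed.

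**The case against.** The strongest reply is that the crossover provisions remain in force. Section 7.0 continues regorafenib until the regorafenib discontinuation criteria are met. The section number printed there is wrong, but the title is that of 8.3, which stops regorafenib alone. Section 13 is the section on treatment and follow-up decisions, and event monitoring is one of the two outcomes that 13.6 permits. Sections 8.12 and 8.13 are worded as what should happen. This stands: the two rules conflict with the crossover provisions; they do not abolish them.

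A reader might also infer three stronger things that the documents do not support.
- *That the notes to Tables 8.22b and 8.23 bar crossover too.* They do not name event monitoring, and 13.6 lets a patient who leaves protocol treatment during the initial phase be re-registered. They are ambiguous, because 8.6 uses protocol treatment for the whole sequence, but they do not by themselves close the route.
- *That sites must apply 8.12 and 8.13 strictly in the first two cycles.* The instruction in 8.0 ("Strictly follow the modifications in the following tables for the first" two cycles) covers tables, and these two rules are numbered text.
- *That an affected patient gets no anti-EGFR drug at all.* Cetuximab and panitumumab are commercially available, and 18.1 provides for recording non-protocol treatment during event monitoring. What is lost is the assigned drug on protocol, with its PFS2 and response data.

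What survives is the literal text of 8.12 and 8.13, its conflict with five other provisions, and the lack of a counterpart in 8.44.

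**Conclusion.** The point holds as an internal inconsistency in two rules that falls on one arm. Followed as written, 8.12 and 8.13 take from the Arm A physician a choice that the Arm B physician keeps.

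The effect is probably small. The range of 0.1 to 2.1 patients rests wholly on assumed rates and shows scale only. The 8.2% comes from a trial of standard dosing and may include stops that 8.3 handles without 8.12 or 8.13, such as grade 4 hypertension or liver criteria. Section 13.6 already permits the same losses in either arm by choice; the defect is a rule that imposes them in one.

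PFS2, stPFS and the sequential response rate are the endpoints mainly touched. A reader might infer from step 5 that OS power is compromised. The documents do not support that: they give neither the share affected nor the survival of such patients. OS by randomised arm stays well defined, and the required events and design power do not change. The wording should still be corrected, because it governs what happens to intolerant Arm A patients and the correction is nearly free.

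**What to change.** Replace the consequence in 8.12 and 8.13 with: *Discontinue regorafenib. If it is the initial treatment (Arm A), the patient may be re-registered for sequential treatment under 6.4 and 13.6 or enter event monitoring, as the treating physician decides. If it is the sequential treatment (Arm B), the patient enters event monitoring.*

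For consistency, in note d to Table 8.22b and notes a and c to Table 8.23, replace the reference to leaving protocol therapy with *discontinue regorafenib (see 8.6 and 13.6)*.

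The cost is a wording amendment to two rules and three notes. Sample size, event target and analysis methods stay as they are. No extra data are needed: the number starting sequential treatment in each arm is already the denominator in 16.325. The change gives both arms the same choice; it does not prevent the losses that 13.6 allows.

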8.3 Criteria for discontinuing treatment with regorafenib

Treatment with regorafenib will be discontinued if any of the following criteria for discontinuation is met:

1. When regorafenib is considered to be ineffective
 - Radiographically confirmed disease progression.
 - Significant worsening of symptoms or physical findings (disease progression should be radiographically confirmed whenever possible).

2. When treatment with regorafenib cannot be continued
 - It is necessary to reduce the dose of regorafenib to less than dose level -2 according to the criteria for dose reduction/modification of treatment.
 - Treatment cannot be resumed within 28 days after modification of treatment due to an adverse event.
 - A 3rd episode of grade 3 hand-and-foot syndrome occurs despite symptomatic treatment and dose reduction of regorafenib.
 - Grade 4 hypertension.
 - Grade 4 or higher increase in AST/ALT, 2nd episode of grade 3 increase in AST/ALT or bilirubin > upper limit of normal x 2 and AST or ALT > upper limit of normal x 3.
 - Other grade 4 non-hematological toxicity.
 - The treating physician decides that treatment with regorafenib cannot be continued due to safety concerns.
3. Patient's request for discontinuation of treatment with regorafenib.
4. After enrollment, the patient is found to be ineligible for the study, and it is concluded that further treatment with regorafenib is detrimental to him/her.
5. Transfer to another institution for any reason during treatment with regorafenib.

8.4 Combination therapy of Anti-EGFR therapy (cetuximab (Cmab) OR panitumumab (Pmab)) and irinotecan

Treatment with cetuximab/panitumumab or irinotecan will be started if it is confirmed that all criteria for treatment are met prior to treatment initiation. If all criteria for starting treatment with Cmab/Pmab are met, but any of the criteria for starting treatment with irinotecan is not met, only Cmab/Pmab can be administered. If the case is reversed, however, irinotecan should not be administered alone (without Cmab/Pmab).

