8.44 Criteria for discontinuing treatment including Cmab or Pmab

Treatment with Cmab/Pmab plus irinotecan or Cmab/Pmab alone will be discontinued if any of the criteria for discontinuation listed below is met. When treatment with irinotecan is discontinued due to an irinotecan-related adverse event, treatment with Cmab/Pmab alone will be continued if none of the following criteria are met:

1. When treatment including Cmab/Pmab is considered to be ineffective
 - Radiographically confirmed disease progression per RECIST 1.1.
 - Significant worsening of symptoms or physical findings (disease progression should be radiographically confirmed wherever possible).
2. When treatment with Cmab/Pmab cannot be continued
 - It is necessary to reduce the dose of Cmab/Pmab to less than dose level -3 according to the criteria for dose reduction/modification of treatment.
 - Treatment cannot be resumed within 28 days after modification of treatment due to an adverse event.
 - The 3rd episode of grade 3 skin toxicity occurs despite symptomatic treatment and dose reduction of Cmab/Pmab.
 - Grade 3 or higher infusion-related reaction related to Cmab/Pmab.
 - Grade 4 non-hematological toxicity.
 - The treating physician concludes that treatment with Cmab/Pmab cannot be continued due to safety concerns.
3. Patient's request for discontinuation of treatment with Cmab/Pmab.
4. After entry, the patient is found to be ineligible for the study, and it is concluded that further treatment including Cmab/Pmab is detrimental to him/her.
5. Transfer to another hospital for any reason during treatment including Cmab/Pmab.

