8.6 Criteria for Discontinuing Protocol Treatment

Protocol treatment will be continued until any of the criteria for discontinuing protocol treatment is met, and the study will be completed when it is decided to discontinue treatment.

1. Any of the criteria for discontinuing initial treatment (regorafenib for patients in Arm A and anti-EGFR±irinotecan for patients in Arm B) is met, and sequential treatment cannot be resumed within 28 days
2. Any of the criteria for discontinuing sequential treatment (anti-EGFR±irinotecan for patients in Arm A and regorafenib for patients in Arm B) is met.
3. Patient's request for discontinuation of protocol treatment.
4. Treating physician's decision

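### Sections 8.12 and 8.13 send patients who cannot continue regorafenib to event monitoring, dropping the re-registration option that other sections give when regorafenib comes first (Arm A); for 8.13 this depends on an undefined 28-day clock

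*Combined protocol and SAP*

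**What the plan says.** Two rules under Section 8.1 of the protocol deal with a patient who cannot stay on regorafenib. Section 8.12: "Patients with dose reductions below 80 mg should go off treatment and go to event monitoring". Section 8.13: "Any patients with toxicities requiring >4 week delay should go off treatment and then to event monitoring". Both apply in either arm, and neither mentions the sequential phase.

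Other sections say what follows when initial treatment stops for intolerance:

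- Section 6.41: "Upon local confirmation of progression or intolerance, patients will be allowed to re-registered to receive the sequential treatment in the treatment arm". The note that opens Section 6.4 limits re-registration to 28 days from documentation of progression or intolerance.
- Section 8.6 item 1 ends protocol treatment when a criterion for stopping initial treatment "is met, and sequential treatment cannot be resumed within 28 days".
- Section 13.6 gives a patient who stops initial treatment for a reason other than progression two routes, at the physician's discretion: re-registration or event monitoring. For a patient already on sequential treatment it gives only survival follow-up.
- Footnote 12 of the Section 4.1 test schedule states re-registration after intolerance as what happens, not as an option.

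Table 8.21 footnote c requires permanent discontinuation after a 4-week delay without recovery, but exempts a patient who is deriving clinical benefit.

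**The concern.** The trial compares two sequences. Regorafenib comes first in Arm A and second in Arm B, so one instruction attached to regorafenib acts at different points of the two strategies. In Arm B, event monitoring after regorafenib is the normal end of protocol treatment. In Arm A it skips the anti-EGFR treatment that completes the randomized sequence.

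A site that works from the regorafenib dose section alone would not learn that re-registration is possible. It would withhold on-protocol anti-EGFR therapy from Arm A patients whom Section 13.6 allows to receive it. What is at stake is adherence to the sequence in one arm, and the composition of the endpoints that depend on the second treatment.

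**Working it through.** No design figure bears on this point. The check compares texts, with short arithmetic on dose and dates.

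**1. Dose rule (8.12).** Treatment starts at 80 mg and moves in 40 mg steps (Sections 7.11, 8.1, 8.11). One step down from the starting dose gives 80 − 40 = 40 mg, which is below 80 mg, so a single reduction in week 1 can trigger the rule. Nothing in this trigger uses up the 28 days of Section 6.4. Side by side, for an Arm A patient:

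| Section | Next step |
|---|---|
| 8.12 | Event monitoring only |
| 13.6 | Re-registration or event monitoring, physician's choice |
| 6.41 | Re-registration allowed |
| 8.6 item 1 | Protocol treatment ends only if sequential treatment cannot follow within 28 days |
| 4.1 footnote 12 | Re-registration |

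Section 8.12 reduces two options to one.

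**2. Delay rule (8.13).** Count the first withheld dose as day 0, and take the rule as met once the delay exceeds 28 days, so on day 29 at the earliest.

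- If intolerance is documented at the start of the hold, the window closes on day 28. Since 28 < 29, re-registration is no longer possible when 8.13 applies, and event monitoring is the right result.
- If intolerance is documented when regorafenib is stopped for good, the window runs to day 29 + 28 = 57. Re-registration is open, and 8.13 removes it as 8.12 does.

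The protocol does not say which date counts. Separately, 8.13 takes every patient with such a delay off treatment, while Table 8.21 footnote c lets a patient deriving clinical benefit continue. That conflict does not depend on the clock.

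**3. Arm by arm.** In Arm B regorafenib is the sequential treatment, so event monitoring agrees with Section 13.6. The list for Arm B's first treatment, Section 8.44, begins "Treatment with Cmab/Pmab plus irinotecan or Cmab/Pmab alone will be discontinued if any of the criteria for discontinuation listed below is met" and never names event monitoring. No rule does to Arm B what 8.12 and 8.13 would do to Arm A.

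**4. Endpoints for an affected Arm A patient.**

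- OS: the patient stays in Arm A, because the Evaluable Population (Section 16.1) requires only some protocol treatment of an eligible, consented, randomized patient with a right-sided tumor.
- stPFS (16.323): censored at the last evaluation before initial treatment stopped, so the censoring is driven by toxicity.
- PFS2 (16.322): absent, because time starts at re-registration.
- Sequential response rate (16.325): absent from the denominator, which counts only patients who began sequential treatment.

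**5. Scale.** Section 16.22 plans 26 evaluable patients per arm, so each affected patient is 1/26 = 3.8% of Arm A. The documents do not give the number affected.

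**The case against.** The strongest reply is that the protocol already covers this patient. Section 13 is the section on treatment and follow-up decisions, and 13.6 expressly permits event monitoring, so 8.12 and 8.13 order nothing that it forbids. Section 6.41 is permissive. Footnote 12 of Section 4.1 itself departs from the discretion in 13.6, so it is weak evidence of the intended rule. The 4.1 schedule has a column for registration to the sequential phase, and Section 18.1 has a form for the end of initial treatment separate from the off-treatment form. Section 8.0 turns the modification tables into guidelines after two cycles. The anti-EGFR drugs and irinotecan are commercial supply even on protocol (Section 19.3), and off-protocol use is not barred. The stPFS, PFS2 and response consequences also arise for any patient in either arm whom a physician sends to event monitoring.

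All of this limits the severity. It does not remove the inconsistency. Sections 8.12 and 8.13 are the regorafenib-specific instructions, and they replace a choice with one outcome. Section 8.0 asks for strict adherence in the first two cycles, and Section 1.5 reports adverse events as most frequent in the first course.

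A reader might also infer a direct contradiction with Section 8.3, which has similar triggers: "It is necessary to reduce the dose of regorafenib to less than dose level -2" and "Treatment cannot be resumed within 28 days after modification of treatment due to an adverse event". The text does not support that. Section 8.3 opens "Treatment with regorafenib will be discontinued if any of the following criteria for discontinuation is met" and is silent on what follows. Matching its dose trigger to 80 mg is also an inference, because regorafenib levels are not numbered: 160 − 2 × 40 = 80 mg fits, while 80 − 2 × 40 = 0 mg does not. Nor do the footnotes to Tables 8.22b and 8.23 that take patients off protocol therapy contradict 13.6, which allows re-registration after going off protocol treatment on the initial treatment. They are only ambiguous.

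**Conclusion.** The point holds for 8.12 without condition. For 8.13 it holds if the 28 days run from the decision to stop regorafenib, and not if they run from the start of the hold; the conflict of 8.13 with Table 8.21 footnote c stands either way. Followed as written, the rules would deny an on-protocol second treatment only in Arm A. That affects adherence to the randomized sequence, censoring in stPFS, and membership of PFS2 and the sequential response rate.

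A reader might go further and infer a biased OS comparison or lost power. The documents give neither the share of Arm A that would meet these rules nor the survival of such patients without on-protocol anti-EGFR therapy. Affected patients remain in the OS analysis and may receive the same drugs off protocol. The OS effect cannot be quantified and may be nil.

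Severity is minor to moderate, and the consequences rest on sites following 8.12 and 8.13 literally.

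**What to change.** Reword 8.12 and 8.13 to:

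> *Discontinue regorafenib. If it is the initial treatment, the patient may be re-registered to sequential treatment per 6.4 and 13.6, with the 28 days counted from the date the decision to stop regorafenib permanently is documented; otherwise the patient goes to event monitoring.*

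In addition:

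- State the same clock start in the note to Section 6.4 and in Section 8.6 item 1.
- Align 8.13 with Table 8.21 footnote c, so that it is clear whether a patient deriving benefit may resume after 4 weeks.
- Correct the cross-reference in Section 4.1 footnote 12 and Section 4.2 footnote 11 from 6.3 (randomization) to 6.4 (sequential phase).

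The cost is a wording amendment and a memo to sites. No new data, procedures or patients are needed.
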